9.6.1.4 Overall Survival

The nonparametric Kaplan-Meier method will be used to estimate the survival curve. Participants without documented death at the time of analysis will be censored at the date of the last known alive date.

9.6.1.5 Analysis Strategy for Key Efficacy Variables

A summary of the primary analysis strategy for the key efficacy variables is provided in [Table 12](#).

Table 12 Analysis Strategy for Key Efficacy Variables

Endpoint/Variable	Statistical Method	Analysis Population	Missing Data Approach
Primary Analyses			
ORR per RECIST 1.1 by BICR	Summary statistics with 95% CI using Exact method based on binomial distribution	APaT	Participants with missing data are considered nonresponders
Secondary Analyses			
DOR per RECIST 1.1 by BICR	Summary statistics using Kaplan-Meier method	Responders in APaT population	Censored according to rules in Table 10
PFS per RECIST 1.1 by BICR	Summary statistics using Kaplan-Meier method	APaT	Censored according to rules in Table 11
OS	Summary statistics using Kaplan-Meier method	APaT	Censored at the date participant last known to be alive
APaT=all participants as treated; BICR=blinded independent central review; DOR=duration of response; ORR=objective response rate; OS=overall survival; PFS=progression-free survival; RECIST 1.1=Response Evaluation Criteria in Solid Tumors.			

9.6.2 Statistical Methods for Safety Analysis

Safety and tolerability will be assessed by clinical review of all relevant parameters including AEs, laboratory parameters, vital signs and ECG measurements. The broad AE categories consisting of the percentage of participants with any AE, a drug-related AE, a serious AE, an AE which is both drug-related and serious, a Grade 3 to 5 AE, a drug-related Grade 3 to 5 AE, and who discontinued due to an AE will be summarized. The number and percentage of participants with increased laboratory toxicity grade shift from baseline will also be provided.

The primary safety analyses will include only events that occur before Second Course treatment.

9.6.3 Demographic and Baseline Characteristics

The number and percentage of participants screened and allocated and the primary reasons for screening failure and discontinuation will be displayed. Demographic variables, baseline characteristics, primary and secondary diagnoses, and prior and concomitant therapies will be summarized by descriptive statistics or categorical tables.

9.7 Interim Analyses

No formal interim analyses are planned for this study.

9.7.1 Efficacy Interim Analysis

No formal interim analysis for efficacy is planned for this study. The final analysis is to be performed approximately 36 months after the last participant is enrolled. Participants will continue to be followed after the final analysis until the overall study ends.

9.7.2 Safety Interim Analysis

The study team will be responsible for periodic safety monitoring and reviews. No formal interim safety analysis will be performed for this study.

9.8 Multiplicity

Since there is no formal hypothesis testing for this estimation study, no multiplicity adjustment is planned.

9.9 Sample Size and Power Calculations

In this study, approximately 152 participants with nccRCC will be enrolled.

Table 13 shows the two-sided 95% confidence intervals for ORR with 152 participants for different observed response rates based on the method of Clopper and Pearson (1934) [Clopper, C. J. and Pearson, E. S. 1934].

Table 13 Two-sided 95% Confidence Intervals for ORR with 152 Participants

Number of Observed Responders	ORR Estimates	95% CI of ORR (%)
53	34.9%	(27.3, 43.0)
61	40.1%	(32.3, 48.4)
64	42.1%	(34.2, 50.4)
68	44.7%	(36.7, 53.0)
CI=confidence interval; ORR=objective response rate.		

9.10 Subgroup Analyses

To determine whether the treatment effect is consistent across various subgroups, the estimate of ORR (with nominal 95% CIs) will be estimated and plotted within each category of the following subgroup variables:

- Geographic region (US, EU, ROW)
- IMDC risk factor (favorable, intermediate, or poor)
- PD-L1 CPS (<1 , ≥ 1)
- Age category (<65 years, ≥ 65 years)
- Sex (female, male)
- Race (white, all others)
- Histologic subtype (papillary, chromophobe, translocation, unclassified)
- Sarcomatoid Feature (with, without)

The consistency of the treatment effect will be assessed using descriptive statistics for each category of the subgroup variables listed above. If the number of participants in a category of a subgroup variable is less than 10% of the APaT population, the subgroup analysis will not be performed for this category of the subgroup variable, and this subgroup variable will not be displayed in the forest plot.

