2.1 Study Rationale

2.1.1 Non-clear Cell Renal Cell Carcinoma

RCC accounts for 3% to 4% of all adult malignancies, representing the sixth most common cancer in men and the eighth most common cancer in women in the US [Siegel, R. L., et al 2020]. Globally in 2018 there were an estimated 403,000 new cases of kidney cancer and 175,000 deaths due to the disease reported [Bray, F., et al 2018].

RCC originates within the renal cortex and is the most common kidney cancer constituting up to approximately 85% of primary renal neoplasms, with a median age at diagnosis of 64 years [National Comprehensive Cancer Network 2019]. Smoking, obesity, and hypertension are established risk factors for RCC development, and several hereditary conditions (eg, von Hippel-Lindau disease) also predispose patients to having an increased risk of developing RCC [National Comprehensive Cancer Network 2019]. The most important prognostic determinants of the 5-year survival rates in RCC are tumor stage, grade, local extent of the tumor, presence of regional nodal metastases, and evidence of metastatic disease at presentation [National Comprehensive Cancer Network 2019]. RCC primarily metastasizes to the lung, bone, liver, lymph nodes, adrenal gland, and brain [Bianchi, M., et al 2012].

At initial diagnosis, approximately two-thirds of patients with RCC present with localized disease and one-third present with unresectable or metastatic disease at diagnosis [Siegel, R. L., et al 2020]. And approximately 20% to 30% of patients with localized tumors will eventually relapse [National Comprehensive Cancer Network 2019].

Recent analyses of the SEER database indicate that the incidence of RCC has been rising on average 0.6% each year and death rates have been falling on average 0.7% each year from 2006 through 2015. [National Cancer Institute 2020]. However, although the 5-year survival for localized RCC is high at 92.6%, the 5-year survival rate for patients with distant metastasis remains dismal at 13.0% [National Comprehensive Cancer Network 2019].

The vast majority of RCC contain a clear cell histology (70% to 80%) with the remainder of cases being summarized as non-clear cell. This heterogeneous group is further subclassified into less common subtypes such as papillary (10% to 15% of all RCCs), chromophobe (5% to 7%), collecting duct (1% to 2%), renal medullary (<1%), and translocation RCC tumors (<1%) [Leibovich, B. C., et al 2010] [Lipworth, L., et al 2016] [Moch, H., et al 2000].

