2.1.3 Rationale for the Use of Pembrolizumab and Lenvatinib in Patients with nccRCC

KEYNOTE-427 Cohort B contains the largest cohort of participants with nccRCC in a clinical trial (n=165) providing proof of concept for clinical activity of pembrolizumab monotherapy in the first-line setting. At the 2-year follow-up, pembrolizumab demonstrated an ORR of 26.7% with a DCR of 43% and a median PFS and OS of 4.2 and 28.9 months, respectively. Clinical activity was demonstrated across key patient subgroups, including IMDC risk groups, histologic subtype, PD-L1 status, and sarcomatoid differentiation.

A single-arm Phase 2 trial of lenvatinib plus everolimus (n=31) demonstrated an ORR of 25.8% and a DCR of 71% with a median PFS of 9.2 months and median OS of 15.6 months. Given the observed ORR of everolimus as reported above, the improved ORR in this study is thought to be primarily due to the lenvatinib component. However, it is noted that in chromophobe subtypes, given the high rates of mTOR pathway alterations, the contribution of everolimus to the clinical activity might be larger.

An open-label, Phase 1b/2 study (E7080-A001-111) of the combination of lenvatinib plus pembrolizumab in participants with select metastatic tumor types, including metastatic ccRCC, is ongoing to assess the safety and efficacy of the combination of lenvatinib plus pembrolizumab. As of a data cutoff date of 12-JAN-2020, 46 of 91 evaluable participants with ccRCC had achieved a confirmed PR for an ORR of 51% with a median DOR of 9.9 months. The safety of the combination was also assessed, with the most common TRAEs ($\geq 30\%$) being fatigue (49%), diarrhea (44%), proteinuria (37%), hypertension (31%), and nausea (31%). No new safety signals were observed beyond what was already known for the combination of pembrolizumab and lenvatinib.

Given the observed efficacy of PD-1/PD-L1 targeted therapies and lenvatinib in the advanced/metastatic RCC population, along with the high unmet medical need in patients specifically with non-clear cell histologies, there is strong rationale to support the exploration of the combination of pembrolizumab and lenvatinib in patients with nccRCC.

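### If enrolment follows the protocol's prevalence figures, the 10% rule in Section 9.10 very probably removes histologic subtype from the ORR forest plot because one listed category, translocation, is rare

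*Combined protocol and SAP*

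**What the plan says.** Section 9.10 of the combined protocol and SAP plans ORR with nominal 95% CIs, estimated and plotted by category, for eight subgroup variables. One of them is "Histologic subtype (papillary, chromophobe, translocation, unclassified".

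The sparse-category rule opens with "If the number of participants in a category of a subgroup variable is less than 10% of the APaT population". The first consequence is that "the subgroup analysis will not be performed for this category of the subgroup variable". The second is "and this subgroup variable will not be displayed in the forest plot". The section also says that consistency will be judged from descriptive statistics for each category. It has no pooling rule and no exemption for histology.

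Section 9.9 sets the size: "In this study, approximately 152 participants with nccRCC will be enrolled". Section 6.3.2 rules out stratification, so no histology mix is fixed by design. Sections 4.1 and 5.2 exclude collecting duct and no other non-clear cell histology.

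**The concern.** The two consequences act at different levels. A programmer following the text would drop the estimate for the sparse category and then remove every category of that variable from the figure. One rare subtype is enough to take the common ones off the plot, which works against the section's stated aim of plotting each category to judge consistency.

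Histology is where this matters most plainly. Section 2.1.1 describes nccRCC as heterogeneous. Section 2.1.3 suggests that chromophobe tumours may respond differently to an mTOR inhibitor. It also cites the earlier pembrolizumab monotherapy cohort in these terms: "Clinical activity was demonstrated across key patient subgroups, including IMDC risk groups, histologic subtype". In a single-arm estimation study whose main result is a pooled ORR, readers will look to the forest plot to see whether one subtype carries the result.

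The category list also leaves a gap. Renal medullary carcinoma is named in Section 2.1.1 and is not excluded, but it has no category, and the plan does not say whether the unclassified level is meant to absorb it.

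**Working it through.** **Inputs**
- Planned N = 152 (Section 9.9), taken as the APaT size.
- Threshold: 10% of APaT (Section 9.10).
- Shares of all RCC (Section 2.1.1): clear cell 70-80%, papillary 10-15%, chromophobe 5-7%, collecting duct 1-2%, renal medullary <1%, translocation <1%.
- Collecting duct excluded (Sections 4.1 and 5.2).

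**The plan's own figures.** The plan states no expected subgroup counts. Its only related figures are the exact (Clopper-Pearson) intervals in Table 13. All four rows reproduce at n = 152; for example, 61/152 = 40.1% (32.3, 48.4).

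**Step 1: count needed.** 0.10 × 152 = 15.2, so a category needs at least 16 participants.

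**Step 2: eligible share of RCC.** Non-clear cell is 20-30% of RCC. Removing collecting duct gives 20 − 2 = 18% up to 30 − 1 = 29%. A smaller denominator comes from adding listed subtypes at their low ends, with translocation at its 1% ceiling: 10 + 5 + 1 = 16%.

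**Step 3: translocation.** Share = 1% ÷ eligible share; expected count = 152 × share; P(≥16) from the exact binomial. Because 1% is a ceiling, the shares and counts are upper limits for each denominator.

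| Eligible share of RCC | Translocation share | Expected of 152 | P(≥16) | P(variable dropped) |
|---|---|---|---|---|
| 29% | 3.4% | 5.2 | 0.00008 | over 99.9% |
| 18% | 5.6% | 8.4 | 0.011 | 98.9% |
| 16% | 6.25% | 9.5 | 0.029 | 97.1% |

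**Step 4: the larger subtypes, on the 18-29% denominators.**
- Papillary: 10/29 = 34% to 15/18 = 83%, or about 52 to 127 participants.
- Chromophobe: 5/29 = 17% to 7/18 = 39%, or about 26 to 59 participants. In the least favourable case, P(<16) = 0.008.

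Both clear 10%. No prevalence is given for the unclassified category, so it cannot be checked; if it too were sparse, the rule would be triggered again.

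**Step 5: sensitivity to the enrolled mix.** At a true translocation share of 8%, P(≥16) = 0.158, so the variable is dropped with probability 84%. At 10%, P(≥16) = 0.453, so 55%. For the expected share to reach 10%, translocation would have to be 0.10 × 18 = 1.8% to 0.10 × 29 = 2.9% of all RCC, above the stated ceiling of 1%.

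**The case against.** **Subtype results are not suppressed.** A reader might infer that the plan hides whether one histology drives the ORR. The text does not support that. Only the category under 10% loses its analysis. Papillary and chromophobe ORRs with intervals are still estimated and can be tabulated. What goes is a group of rows in a figure. This objection stands and limits the point.

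**The clause may be a drafting slip.** The first consequence works at category level and the section opens by promising a plot by category, so the last clause may have been meant for the category too. That is possible, but the words say variable, and the correction needed is the same.

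**The prevalences are for RCC overall.** The trial enrols previously untreated Stage IV patients, and the documents give no histology mix for them. This stands: the probabilities are conditional on the all-RCC figures and on treating enrolment as a random draw. Nothing in the documents points to enrichment, but nothing rules it out.

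**Omitting a tiny category is defensible.** With 4 responders of 8, the exact 95% CI runs from about 16% to 84%. That is a fair reason not to analyse translocation alone. It is no reason to take papillary and chromophobe off the plot.

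**Other variables.** A reader might extend the point to IMDC risk, region or sarcomatoid feature. The rule would act on them in the same way, but the documents give no prevalences for them, so no such claim can be made.

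**Conclusion.** The point holds in a limited form. Taken literally, Section 9.10 lets one sparse category remove its whole variable from the forest plot, which defeats the section's own plan to plot ORR by category. On the protocol's figures, histologic subtype would be removed with probability of about 97% or more. That rests on three assumptions: APaT is 152, enrolment mirrors the all-RCC prevalences, and the eligible share is 16-29% of RCC. The result is not a guaranteed floor; at a true share of 8% or 10% it falls to 84% or 55%.

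The severity is minor to moderate. This is a descriptive analysis in a study without hypothesis tests (Section 9.3). A reader might infer that the primary result is at risk. It is not: participants of every enrolled histology who receive at least one dose stay in APaT, and the primary ORR and its interval are unchanged.

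**What to change.** In the last clause of the rule in Section 9.10, replace the reference to the subgroup variable with a reference to the category, so that a category under 10% of APaT is left out of the plot while the variable and its categories of 10% or more remain. For histology, pool sparse subtypes, together with eligible ones that have no listed category such as renal medullary, into a named 'other' category, or list them as responders/n. State whether the unclassified level is meant to hold any of these.

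This is one changed sentence plus one added category. Section 9 already provides for recording such changes in the sSAP before the final database lock, and settling it by then avoids a post hoc choice of which subtypes to show. The cost is one or more wide intervals, or an 'other' row that mixes different tumours and should be read with that in mind.

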9.11 Compliance (Medication Adherence)

Drug accountability data for study treatment will be collected during the study. Any deviation from protocol-directed administration will be reported.

9.12 Extent of Exposure

Extent of Exposure for a participant is defined as the number of cycles and number of days for which the participant receives the study treatment. Summary statistics will be provided on the extent of exposure for the overall study treatment, and for pembrolizumab and lenvatinib separately, for the APaT population.

10 SUPPORTING DOCUMENTATION AND OPERATIONAL CONSIDERATIONS

10.1 Appendix 1: Regulatory, Ethical, and Study Oversight Considerations

10.1.1 Code of Conduct for Clinical Trials

Merck Sharp & Dohme LLC, Rahway, NJ, USA (MSD)

Code of Conduct for Interventional Clinical Trials

I. Introduction

A. Purpose

MSD, through its subsidiaries, conducts clinical trials worldwide to evaluate the safety and effectiveness of our products. As such, we are committed to designing, implementing, conducting, analyzing, and reporting these trials in compliance with the highest ethical and scientific standards. Protection of participants in clinical trials is the overriding concern in the design and conduct of clinical trials. In all cases, MSD clinical trials will be conducted in compliance with local and/or national regulations (including all applicable data protection laws and regulations), and International Council for Harmonisation Good Clinical Practice (ICH-GCP), and also in accordance with the ethical principles that have their origin in the Declaration of Helsinki.

B. Scope

Highest ethical and scientific standards shall be endorsed for all clinical interventional investigations sponsored by MSD irrespective of the party (parties) employed for their execution (e.g., contract research organizations, collaborative research efforts). This Code is not intended to apply to trials that are observational in nature, or which are retrospective. Further, this Code does not apply to investigator-initiated trials, which are not under the full control of MSD.

II. Scientific Issues

A. Trial Conduct

1. Trial Design

Except for pilot or estimation trials, clinical trial protocols will be hypothesis-driven to assess safety, efficacy and/or pharmacokinetic or pharmacodynamic indices of MSD or comparator products. Alternatively, MSD may conduct outcomes research trials, trials to assess or validate various endpoint measures, or trials to determine patient preferences, etc.

The design (i.e., participant population, duration, statistical power) must be adequate to address the specific purpose of the trial and shall respect the data protection rights of all participants, trial site staff and, where applicable, third parties. Participants must meet protocol entry criteria to be enrolled in the trial.

2. Site Selection

MSD selects investigative sites based on medical expertise, access to appropriate participants, adequacy of facilities and staff, previous performance in clinical trials, as well as budgetary considerations. Prior to trial initiation, sites are evaluated by MSD personnel (or individuals acting on behalf of MSD) to assess the ability to successfully conduct the trial.

3. Site Monitoring/Scientific Integrity

Investigative trial sites are monitored to assess compliance with the trial protocol and Good Clinical Practice (GCP). MSD reviews clinical data for accuracy, completeness, and consistency. Data are verified versus source documentation according to standard operating procedures. Per MSD policies and procedures, if potential fraud, scientific/research misconduct, privacy incidents/breaches or Clinical Trial-related

Significant Quality Issues are reported, such matters are investigated. When necessary, appropriate corrective and/or preventative actions are defined and regulatory authorities and/or ethics review committees are notified.

B. Publication and Authorship

Regardless of trial outcome, MSD commits to publish the primary and secondary results of its registered trials of marketed products in which treatment is assigned, according to the pre-specified plans for data analysis. To the extent scientifically appropriate, MSD seeks to publish the results of other analyses it conducts that are important to patients, physicians, and payers. Some early phase or pilot trials are intended to be hypothesis-generating rather than hypothesis testing; in such cases, publication of results may not be appropriate since the trial may be underpowered and the analyses complicated by statistical issues such as multiplicity.

MSD's policy on authorship is consistent with the recommendations published by the International Committee of Medical Journal Editors (ICMJE). In summary, authorship should reflect significant contribution to the design and conduct of the trial, performance or interpretation of the analysis, and/or writing of the manuscript. All named authors must be able to defend the trial results and conclusions. MSD funding of a trial will be acknowledged in publications.

III. Participant Protection

A. Regulatory Authority and Ethics Committee Review (Institutional Review Board [IRB]/Independent Ethics Committee [IEC])

All protocols and protocol amendments will be submitted by MSD for regulatory authority acceptance/authorization prior to implementation of the trial or amendment, in compliance with local and/or national regulations.

The protocol, protocol amendment(s), informed consent form, investigator's brochure, and other relevant trial documents must be reviewed and approved by an IRB/IEC before being implemented at each site, in compliance with local and/or national regulations. Changes to the protocol that are required urgently to eliminate an immediate hazard and to protect participant safety may be enacted in anticipation of ethics committee approval. MSD will inform regulatory authorities of such new measures to protect participant safety, in compliance with local and/or national regulations.

B. Safety

The guiding principle in decision-making in clinical trials is that participant welfare is of primary importance. Potential participants will be informed of the risks and benefits of, as well as alternatives to, trial participation. At a minimum, trial designs will take into account the local standard of care.

All participation in MSD clinical trials is voluntary. Participants enter the trial only after informed consent is obtained. Participants may withdraw from an MSD trial at any time, without any influence on their access to, or receipt of, medical care that may otherwise be available to them.

C. Confidentiality

MSD is committed to safeguarding participant confidentiality, to the greatest extent possible, as well as all applicable data protection rights. Unless required by law, only the investigator, Sponsor (or individuals acting on behalf of MSD), ethics committee, and/or regulatory authorities will have access to confidential medical records that might identify the participant by name.

D. Genomic Research

Genomic research will only be conducted in accordance with a protocol and informed consent authorized by an ethics committee.

IV. Financial Considerations

A. Payments to Investigators

Clinical trials are time- and labor-intensive. It is MSD's policy to compensate investigators (or the sponsoring institution) in a fair manner for the work performed in support of MSD trials. MSD does not pay incentives to enroll participants in its trials. However, when enrollment is particularly challenging, additional payments may be made to compensate for the time spent in extra recruiting efforts.

MSD does not pay for participant referrals. However, MSD may compensate referring physicians for time spent on chart review and medical evaluation to identify potentially eligible participants.

B. Clinical Research Funding

Informed consent forms will disclose that the trial is sponsored by MSD, and that the investigator or sponsoring institution is being paid or provided a grant for performing the trial. However, the local ethics committee may wish to alter the wording of the disclosure statement to be consistent with financial practices at that institution. As noted above, all publications resulting from MSD trials will indicate MSD as a source of funding.

C. Funding for Travel and Other Requests

Funding of travel by investigators and support staff (e.g., to scientific meetings, investigator meetings, etc.) will be consistent with local guidelines and practices.

V. Investigator Commitment

Investigators will be expected to review MSD's Code of Conduct as an appendix to the trial protocol, and in signing the protocol, agree to support these ethical and scientific standards.

